	Febrile neutropenia: grade 4 neutropenia with fever > 38.5 °C both sustained over a 24 hour period.
	Neutropenic infection: grade ≥ 3 neutropenia with grade ≥ 3 infection
	Anemia \geq grade 3
	Grade > 4 thrombocytopenia or grade ≥ 3 thrombocytopenia and grade ≥ 3 hemorrhage
Nonhematologic	Grade 3 or 4 nonhematologic toxicity with the following exceptions: 
 Nausea, vomiting or diarrhea for < 48 hours^a Asymptomatic electrolyte abnormalities that are corrected to grade 1 or better in < 48 hours^b

^aPatients with related grade 3 or 4 diarrhea, nausea or vomiting for ≥ 48 hours despite optimal medical therapy will require a one-level dose-reduction of TRC105.

^bPatients with related grade 3 or 4 electrolyte abnormalities that persist for ≥ 48 hours will require a one-level dose reduction of TRC105.

Up to 15 patients with advanced renal cell carcinoma will be treated at the weekly dosing MTD (or top dose level if a MTD is not determined) to further characterize safety and tolerability. At least 6 patients with advanced renal cell carcinoma will be treated at the every two week dosing MTD (or top dose level if a MTD is not determined).

Phase 2:

This is a multicenter, randomized, phase 2 study of TRC105 in combination with standard dose axitinib in patients with advanced or metastatic renal cell carcinoma. Patients will be stratified by performance status (PS = 0 vs. PS = 1) and centrally randomized in a 1:1 ratio to one of the following treatment arms: TRC105 in combination with standard dose axitinib vs. standard dose axitinib, following documented progression on one prior VEGF inhibitor. All patients will initially receive axitinib 5 mg twice daily; patients randomized to receive TRC105 will receive TRC105 at 3 mg/kg on day 1, 7 mg/kg on day 4, and 10 mg/kg on day 8 and weekly thereafter.

TRC105 may be administered every two weeks starting with cycle 2 day 1 but **ONLY AFTER COHORT 3 AND 4 IN THE PHASE 1B ARE COMPLETE AND THE SPONSOR SENDS NOTIFICATION TO PROCEED WITH EVERY TWO WEEK DOSING.**

- Axitinib dosing will begin on cycle 1 day 1 and twice daily thereafter.
- TRC105 will be administered weekly during cycle 1.
 - The first weekly TRC105 dose will be split into two doses whereby 3 mg/kg is administered on cycle 1 day 1 and the balance is administered on cycle 1 day 4.
- Starting on cycle 2 day 1 and beyond, TRC105 may be administered every two weeks on days 1 and 15.

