4.1.1.2. Phase 2 Overview

This is a multicenter, randomized, phase 2 study of TRC105 in combination with standard dose axitinib in patients with advanced or metastatic renal cell carcinoma. Patients will be stratified by performance status (PS = 0 vs. PS = 1) and centrally randomized to one of the following treatment arms: TRC105 in combination with standard dose axitinib vs. standard dose axitinib, following documented progression on one prior VEGF inhibitor. All patients will initially receive axitinib 5 mg twice daily; patients randomized to receive TRC105 will receive TRC105 at 3 mg/kg on day 1, 7 mg/kg on day 4, and 10 mg/kg on day 8 and weekly thereafter.

TRC105 may be administered every two weeks starting with cycle 2 day 1 but **ONLY AFTER COHORT 3 AND 4 IN THE PHASE 1B ARE COMPLETE AND THE SPONSOR SENDS NOTIFICATION TO PROCEED WITH EVERY TWO WEEK DOSING.**

- Axitinib dosing will begin on cycle 1 day 1 and twice daily thereafter
- TRC105 at 10 mg/kg will be administered weekly during cycle 1.
 - The first weekly TRC105 dose will be split into two doses whereby 3 mg/kg is administered on cycle 1 day 1 and the balance is administered on cycle 1 day 4.
- Starting on cycle 2 day 1 and beyond, TRC105 may be administered every two weeks on days 1 and 15 at either 15 mg/kg or 20 mg/kg

Patients **in both arms** who tolerate axitinib for at least two consecutive weeks with no adverse reactions > Grade 1 considered clinically significant (according to the Common Toxicity Criteria for Adverse Events [CTCAE]), will, at the discretion of their treating physician, have the axitinib dose increased to 7 mg twice daily beginning on cycle 2 day 1, unless the patient's blood pressure is > 150/90 or the patient is receiving more than one antihypertensive medication. Subsequently, with the same criteria, patients who tolerate the axitinib dose of 7 mg twice daily for at least two consecutive weeks may have the axitinib dose increased to a maximum of 10 mg twice daily beginning with cycle 3 day 1. Dose reductions of axitinib and TRC105 are allowed per patient tolerance.

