The best response (CR, PR, SD or PD according to RECIST 1.1 and according to Choi criteria) for each patient with measurable disease who received at least one dose of study drug will be listed by cohort and response rate (CR or PR) between the two arms will be compared by Chi-square test or Fisher exact test. Stable disease will be defined as lack of tumor progression lasting for 2 cycles or longer. Additional analysis will be conducted based on duration of response, defined from the time to first response (CR or PR) to disease progression and will be compared between arms using Kaplan Meier methods. Other secondary analysis would include disease stability rate (DSR) defined as the percent of subjects in ITT population with CR, PR and SD at 12 weeks, and will be compared by Chi-square test or Fisher exact test.

All AEs with an onset after initiation of treatment will be considered as treatment-emergent AEs. A preexisting condition that worsens during the treatment period will also be considered as a treatment emergent AE. All AEs will be coded by system organ class (SOC) and preferred term using NCI CTCAE (MedDRA) version 4.0.

The number and percentage of patients with the following types of treatment-emergent AEs will be summarized for each study arm: common and serious AEs, AEs related to study medication, AEs resulting in study discontinuation, and clinically significant laboratory abnormalities. Laboratory data will be summarized for baseline, treatment visits and change from baseline as appropriate for each arm. Non-treatment-emergent serious AEs will be described separately. Deaths will be reported with demographic information. Comparison of categorical values will be made by Chi-square or Fisher exact test and of continuous variables will be made by Student t test.

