11.1 Primary Endpoint

The primary endpoint for efficacy in Phase 2 will be PFS. For Phase 2, PFS is defined as time from randomization to either first disease progression (by RECIST 1.1) or death from any cause. For Phase 1, PFS is defined from the date of consent to either first disease progression by RECIST 1.1 or death from any cause.

For the purpose of analysis for patients who are alive at the time of analysis and have not had disease progression, the following rules will apply:

- (1) The patient will be censored on the date of the last tumor assessment documenting absence of progressive disease
- (2) If the patient was given antitumor treatment other than study drug treatment, the patient will be censored as of the date of the last tumor assessment prior to initiating that antitumor therapy
- (3) If the patient was removed from study for toxicity or other reason, the patient will be censored as of the date of the last tumor assessment on study.

With regard to missed tumor assessments:

- (1) In the event of one missed tumor assessment followed by a subsequent assessment of progressive disease (PD), the subsequent PD assessment qualifies as objective tumor progression.
- (2) In the event of more than one consecutive missing tumor assessment followed by a subsequent assessment of PD, the patient will be censored at the last adequate tumor assessment. If individual scans are performed on different dates, but contribute to the same overall assessment, the date of the earliest scan will be used.

The PFS distributions in the two arms will be summarized using the Kaplan-Meier method. The distributions will be compared using a stratified (by the randomization stratification factor) log-rank test at the one-sided $\alpha=0.10$ level of significance.

Additional exploratory analyses of PFS will be conducted in subgroups defined based on number of prior therapies (one, two or three), ECOG performance status, and the biomarkers TGF- β receptor III and osteopontin. The same methods are for the primary analysis (Kaplan-Meier

survival estimation, log rank tests) will be used. The effects of these covariates may also be assessed using Cox proportional hazards regression models.

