The best response (CR, PR, SD or PD according to RECIST 1.1 and according to Choi criteria) for each patient with measurable disease who received at least one dose of study drug will be listed by cohort and response rate (CR or PR) between the two arms will be compared using Pearson's chi-square test or Fisher's exact test. Stable disease will be defined as lack of tumor progression lasting for 2 cycles or longer. Additional analysis will be conducted based on duration of response, defined from the time to first response (CR or PR) to disease progression and will be compared between arms using Kaplan Meier methods. Other secondary analysis would include disease stability rate (DSR) defined as the percent of subjects in ITT population with CR, PR and SD at 16 weeks, and will be compared using Pearson's chi-square test or Fisher's exact test.

The primary Phase 2 endpoint of PFS will be determined based on objective tumor assessments made by Central Radiographic Review according to RECIST version 1.1. PFS will also be determined based on investigator assessment. Treatment decisions will be made by the investigator based on application of RECIST 1.1. Supportive analyses will be performed based on investigator assessments of disease response and progression. In cases where Central Radiographic Review assessment of response conflict with investigator assessment the data will be censored as it related to the endpoint.

The clinical response of the study treatment will be assessed by a comparative evaluation of computed tomography (CT) or magnetic resonance imaging (MRI) scans prior to enrollment into the study and every 8 weeks using RECIST 1.1 (primary endpoint) or Choi criteria (secondary endpoint).

A listing will be provided for best overall response, i.e., CR, PR, SD, PD or NA (not assessable due to missing or incomplete assessments or inconsistent assessment methods) for each patient. A listing or figure will also be provided for duration of PFS and sum of the diameters for target lesions over time in patients. The listings for best overall response and PFS will compare to overall response and PFS of treatments received prior to study entry, including the most recent treatment that included a VEGF inhibitor.

12. Safety Analyses

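### Response rate and 16-week disease stability rate are compared without the ECOG PS stratification used in randomisation and in the PFS test; a stratified test costs almost nothing and gains a little

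*SAP*

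**What the plan says.** **Randomisation.** The Protocol synopsis states "Patients will be stratified by performance status (PS = 0 vs. PS = 1) and centrally randomized in a 1:1 ratio"; Protocol 4.1.1.2 repeats the stratification. Neither document states a block size or any other balancing method, and Protocol 6.5 describes only manual enrolment by the sponsor.

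**Primary endpoint.** SAP 11.1 follows the design: "The distributions will be compared using a stratified (by the randomization stratification factor) log-rank test at the one-sided" 0.10 level.

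**Binary secondary endpoints.** The same SAP section says that "response rate (CR or PR) between the two arms will be compared using" Pearson's chi-square or Fisher's exact test. For DSR it counts patients "with CR, PR and SD at 16 weeks, and will be compared using Pearson's chi-square test or Fisher's exact test". Protocol 10.5.2 agrees on response: "response rate (CR or PR) between the two arms will be compared by Chi-square test or Fisher exact test". Neither document offers a stratified test, an adjusted model or a stratified rate difference for either endpoint.

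**Status.** SAP 2.2.2 words both as secondary objectives of estimation. No alpha, sidedness, power or testing order is given for them.

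**The concern.** The plan stratifies by PS at randomisation and in the PFS test, then leaves it out of the response comparisons without giving a reason. This matters if PS predicts response. The Pearson test uses the pooled variance, which includes the spread between PS groups. When both arms hold the same PS mix, that spread does not contribute to the error of the treatment difference, so the variance is overstated. When the mix is not held equal, the unstratified comparison is open to chance PS imbalance, which a stratified test removes.

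At stake are some power on two secondary endpoints, consistency with the primary analysis, and an estimate of the between-arm difference. The objectives call for estimation, but SAP 11.1 names only tests for these comparisons.

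**Working it through.** **The plan's own figure.** None exists for response or DSR. The only design figure is 115 PFS events (SAP 4.2). It reproduces: with (z₀.₉₀ + z₀.₈₀)² = 4.508, Schoenfeld gives 4 × 4.508 / (ln 0.67)² = 112.4, so 113; Freedman gives (1.67/0.33)² × 4.508 = 115.4, so 116. Nothing below affects it.

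**Inputs from the documents.**
- About 150 patients randomised 1:1, so 75 per arm (SAP 4.2).
- Axitinib response rate 19.4% (Protocol Table 3, second-line trial). It is the only axitinib response rate given, and a rough anchor: Protocol 2.1.1 notes that many of those patients had no prior VEGFR-directed therapy.
- Control median PFS 4.8 months (SAP 4.2). Under exponential PFS, the proportion progression-free at 16 weeks (3.68 months) is exp(−0.693 × 3.68/4.8) = 0.59, used as control DSR.

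**Assumptions not in the documents.** The share of PS 1 patients, the rates by PS, the common odds ratio (OR), and two-sided 0.05.

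**Formulas.** Pearson: Z = (p̂_T − p̂_C) / √[p̂(1 − p̂)(1/75 + 1/75)]. CMH, per stratum with a responders among t treated patients, c controls, m responders in all and T = t + c: d = a − mt/T, V = tcm(T − m)/[T²(T − 1)], Z = Σd/√ΣV.

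**Why the direction is as stated.** With a share w in PS 0 and balance forced, the ratio of true to assumed null variance is R = [w·p₀(1 − p₀) + (1 − w)·p₁(1 − p₁)] / [p(1 − p)], where p is the marginal rate. For response of 25% in PS 0 and 11% in PS 1 with w = 0.6: p = 0.194 and R = 0.1517/0.1564 = 0.970. For 45% and 8% with w = 0.5: p = 0.265 and R = 0.1606/0.1948 = 0.824, so the approximate size is 2[1 − Φ(1.96/√0.824)] = 0.031.

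**Simulation, balance forced within strata, two-sided 0.05** (rows 1–6: 45 PS 0 and 30 PS 1 per arm, OR 2.78 for response and 2.6 for DSR; rows 7–9: half PS 0, OR 2.5)

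| Endpoint, control rate PS 0 / PS 1 | Power, Pearson | Power, CMH | Gain (points) | Size, Pearson |
|---|---|---|---|---|
| Response 22% / 15.5% | 79.3% | 79.7% | 0.4 | 0.050 |
| Response 25% / 11% | 76.6% | 78.2% | 1.6 | 0.048 |
| DSR 64% / 51.5% | 74.5% | 75.2% | 0.7 | 0.054 |
| DSR 69% / 44% | 71.6% | 74.0% | 2.4 | 0.048 |
| Response 30% / 3.5% (extreme) | 65.3% | 72.0% | 6.7 | 0.039 |
| DSR 79% / 29% (extreme) | 55.3% | 66.0% | 10.7 | 0.028 |
| Response 25% / 12% | 65.5% | 67.0% | 1.5 | 0.048 |
| Response 35% / 10% (strong) | 62.7% | 67.7% | 5.0 | 0.040 |
| Response 45% / 8% (strong) | 55.0% | 64.7% | 9.7 | 0.031 |

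CMH size is about 0.050 throughout, except 0.053 for DSR 64% / 51.5%. There both tests sit slightly above nominal, so that excess does not come from omitting the stratum.

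**Variations on the modest-to-moderate settings.**
- Simple randomisation within strata: Pearson size is 0.050–0.051, so there is no conservatism. The gain from CMH runs from −0.2 to 1.9 points.
- One-sided 0.10, the level used for PFS: −0.2 to +1.1 points.
- Share of PS 1 between 31% and 51%: similar results.
- Fisher in place of Pearson: size 0.031 (response) and 0.038 (DSR) with no PS effect at all, and a cost of about 5–6 points of power against Pearson.

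**The case against.** The strongest reply is that unstratified tests of secondary binary endpoints are valid, that these endpoints are framed as estimation in a phase 2 trial, and that no sample size or decision rule depends on their p-values. Conservatism cannot create a false positive. All of this stands, and it is why the point is low in severity.

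A reader might infer more: that the plan simply wastes power and that its tests are conservative. The documents do not support that as a flat statement.
- It needs a material PS effect on response, and no response or stability rate by PS is given. Nor do the documents say why PS was chosen as the stratum; that it is prognostic for response is an inference.
- The conservatism also needs enforced balance within strata, and no method is stated. SAP 11.1 adds doubt by listing best response for treated patients with measurable disease, while SAP 3.2 places the response-rate analysis in all randomised patients. In a treated subset, balance is not guaranteed.
- The large losses arise only with contrasts such as 45% vs 8%, which have no basis in the documents. Among the half-PS-0 settings, the one whose marginal control rate (18.5%) lies closest to 19.4% gains 1.5 points.

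It is also fair to say that the open choice between Pearson and Fisher matters more than stratification under modest PS effects. That supports naming one main test; it is no argument for leaving the stratum out.

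**Conclusion.** The inconsistency is real and appears in both documents: PS stratifies the randomisation and the PFS test but not the response-rate and DSR comparisons. If PS predicts response, the unstratified tests give up some power, and they are also conservative if balance within strata is enforced.

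Under modest-to-moderate assumed PS effects the loss is about 0 to 2.4 points at two-sided 0.05, and the difference is −0.2 to +1.1 points at one-sided 0.10. A loss of 5 to 11 points appears only under strong assumed effects. These sizes rest on assumed rates by PS, odds ratios and PS mix, and on an assumed alpha, because the documents give none of these for response or DSR.

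This is a free improvement of low severity. No stated figure changes, and the primary conclusion is unaffected.

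**What to change.** In SAP 11.1, replace the two unstratified comparisons with a Cochran-Mantel-Haenszel test stratified by the randomisation factor (ECOG PS 0 vs 1), for response rate and for 16-week DSR. Report the PS-stratified rate difference with its 95% confidence interval, which also serves the estimation objective. Keep the unstratified test as supportive, and state in advance whether it is Pearson or Fisher.

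Use the same wording in Protocol 10.5.2 if it is amended. That section gives DSR at 12 weeks, against 16 weeks in the SAP and in the Protocol's own objectives, so the time point needs to be reconciled too.

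The cost is one SAP sentence and one line of code. PS is already needed for every randomised patient in order to stratify. The most that CMH gave up in any setting run was about 0.2 points of power.

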10.5. Analysis of Primary and Secondary Objectives

10.5.1. Phase 1b

For each cohort, DLTs will be summarized by category (hematologic and non-hematologic) and by MedDRA preferred term.

All AEs with an onset after initiation of treatment will be considered as treatment-emergent AEs. A preexisting condition that worsens during the treatment period will also be considered as a treatment emergent AE. All AEs will be coded by system organ class (SOC) and preferred term using NCI CTCAE (MedDRA) version 4.0.

The number and percentage of patients with the following types of treatment-emergent AEs will be summarized: common and serious AEs, AEs related to study medication, AEs resulting in study discontinuation, and clinically significant laboratory abnormalities. Non-treatment-emergent serious AEs will be described separately. Deaths will be reported with demographic information.

10.5.2. Phase 2

The primary endpoint for efficacy will be PFS, defined as time from randomization to either first disease progression (per independent radiology review of images by RECIST) or death from any cause. PFS will be censored on the day following the date of the last tumor assessment documenting absence of progressive disease for patients who do not have objective tumor progression and are still on study at the time of analysis, are given antitumor treatment other than the study treatment, are removed from study follow-up prior to documentation of objective tumor progression, died of non-cancer causes including death due to an unknown cause in the absence of documented disease progression.

The PFS distributions in the two arms will be summarized using the Kaplan-Meier method. The distributions will be compared using a stratified (by performance status) log-rank test at the one-sided $\alpha=0.10$ level of significance.

Additional exploratory analyses of PFS will be conducted in subgroups defined based on number of prior therapies (one, two or three). The same methods as for the primary analysis (Kaplan-Meier survival estimation, log rank tests) will be used. The effects of these covariates may also be assessed using Cox proportional hazards regression models.

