2.1.2. Secondary Objective(s)

The secondary objectives are to evaluate pharmacokinetics (PK), immunogenicity and activity of the monoclonal antibody TRC105. The specific objectives of the efficacy analysis are:

- To look for preliminary evidence of antitumor activity when TRC105 is added to axitinib, by assessing response rate and progression-free survival
- To characterize the pharmacokinetic profile of TRC105 when given with axitinib
- To evaluate TRC105 immunogenicity by measuring anti-product antibody (APA) formation
- To explore the pharmacodynamic changes in circulating angiogenic biomarkers following treatment with TRC105 and axitinib

2.2. Phase 2

2.2.1. Primary Objective:

- To estimate the progression-free survival (PFS) of patients with advanced or metastatic RCC by RECIST 1.1 in patients treated with axitinib and TRC105 compared to those treated with axitinib alone, following failure of one prior VEGF inhibitor.

2.2.2. Secondary Objective(s):

- To estimate response rate by RECIST 1.1 and Choi criteria, including duration of response by RECIST 1.1 and Choi criteria
- To estimate the disease control rate (CR + PR + SD) at 16 weeks by RECIST1.1 and Choi criteria
- To determine the frequency and severity of adverse events as assessed by NCI CTCAE (Version 4.0)
- To evaluate TRC105 immunogenicity as measured by Anti-Product Antibody (APA) concentrations
- To explore the effects of TRC105 on circulating angiogenic protein biomarkers
- To characterize the pharmacokinetic profile of TRC105 and axitinib

3. Study Design

3.1. Phase 1

This is a multicenter, open-label, nonrandomized, phase 1b, dose-finding study of TRC105 in combination with standard dose axitinib in patients with advanced renal cell carcinoma. Escalating doses of i.v. TRC105 will be administered weekly beginning with Dose Level 1 in combination with oral axitinib given twice daily of each 28 day cycle. Additional intermediate doses (below the MTD established during the trial) may be explored based upon clinical, PK, and/or biomarker data.

Cohort	Number of Evaluable Subjects	Axitinib mg p.o., BID days 1-28	TRC105 mg/kg IV
-1	3-6	5	6 ^a
1 (starting dose)	3-6	5	8 ^a
2	3-6	5	10 ^a
Expanded Cohort 1	9-12 (up to 15 total at the MTD)	5	10 ^a
3	3-6	5	
 • 10 mg/kg weekly during cycle 1^b • 15 mg/kg every two weeks beginning with cycle 2 day 1^b

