The study population for safety will include all patients receiving at least a portion of one dose of study drug (TRC105 or axitinib). The study population for efficacy will include all randomized patients (intention to treat). The primary endpoint is PFS and the primary analysis will compare the TRC105 and control groups using a one-sided, stratified (by the randomization stratification factor) log-rank test at the $\alpha=0.10$ level of significance. The primary analyses of efficacy endpoints dependent on disease assessments (PFS, ORR and DR) will be performed in the intent-to-treat (ITT) population based on results of the central review of disease response and progression. Supportive analyses will be performed based on investigator assessments of disease response and progression. Pre-planned assessments of the primary endpoint will additionally be done based on number of prior therapies (one, two or three) and other known prognostic factors.

An interim analysis for futility will be conducted by the DMC when 55 events have occurred. At the interim analysis, the conditional power based on the observed hazard ratio (HR) will be estimated. If the conditional power is less than 25%, the DMC may recommend to the sponsor that the study be terminated for futility. However, this interim analysis will not consider the possibility of early termination on the basis of superior efficacy.

4. Sample Size Determination

4.1. Phase 1

The number of patients to be evaluated in this study is based primarily on sound clinical considerations established in dose-finding designs in Oncologic studies. This 3+3 dose escalation trial is expected to enroll approximately 18 patients. The final sample size will depend on the number of DLTs observed at the different dose levels.

4.2. Phase 2

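### Duration of response ends only at progression, so a response cut short by death is implicitly censored, and the by-arm comparison covers responders only

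*SAP*

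**What the plan says.** SAP 11.1 says that duration of response is "defined from the time to first response (CR or PR) to disease progression and will be compared between arms using Kaplan Meier methods". Protocol 10.5.2 matches it: "duration of response, defined from the time to first response (CR or PR) to disease progression", again with a Kaplan-Meier comparison by arm.

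PFS in SAP 11.1 is wider, running as the "time from randomization to either first disease progression (by RECIST 1.1) or death from any cause". The SAP's censoring rules follow the PFS definition and are limited to "patients who are alive at the time of analysis and have not had disease progression, the following rules will apply". Protocol 10.5.2 also counts death from any cause in its PFS definition, but its censoring sentence then lists patients who "died of non-cancer causes including death due to an unknown cause in the absence of documented disease progression". Neither document writes a censoring rule for duration of response.

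On the population, SAP 3.2 says that the primary analyses of "efficacy endpoints dependent on disease assessments (PFS, ORR and DR) will be performed in the intent-to-treat (ITT) population", and protocol 10.2.1 agrees. The endpoint belongs to a secondary estimation objective in SAP 2.2.2: "To estimate response rate by RECIST 1.1 and Choi criteria, including duration of response by RECIST 1.1 and Choi criteria". Protocol 3.1.2.2 has the same objective, with duration by RECIST 1.1 only.

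**The concern.** There are two separate difficulties.

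The first is the end of the clock. Death normally ends a response as surely as progression does. If progression is the only event, a Kaplan-Meier analysis has nowhere to put a death without progression except among the censored. The estimate then treats that patient as though the response could have continued. If such deaths were more frequent in one arm, that arm would look more durable than it is.

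The second is the start of the clock. It starts at first response, so a non-responder has no time to contribute. Who responds is settled after randomisation and may depend on treatment. A difference between arms in duration can therefore reflect who responded as well as how long responses lasted. The ITT label suggests a protection that this comparison does not have.

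**Working it through.** **Plan's own figure.** The documents give no design figure for duration of response. The only related one is 115 PFS events (one-sided alpha 0.10, 80% power, hazard ratio 0.67, 1:1). It reproduces:

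- Schoenfeld: 4 × (1.2816 + 0.8416)² / (ln 0.67)² = 112.4, so 113.
- Freedman: (1.2816 + 0.8416)² × (1.67/0.33)² = 115.5, so 116.

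Nothing below changes that figure.

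**Rules side by side.**

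| | Events | Censoring rule |
|---|---|---|
| PFS, SAP 11.1 | progression or death from any cause | written, for living patients without progression |
| PFS, protocol 10.5.2 | progression or death from any cause | written, but includes non-cancer and unknown-cause deaths without documented progression |
| Duration of response, both documents | progression | none |

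**Effect of leaving deaths out.** Assume independent exponential hazards after response, with total hazard L for progression or death and a share d of it due to death without progression. The median counting both events is ln 2 / L. Censoring deaths leaves hazard (1 - d)L and median ln 2 / [(1 - d)L]. The ratio is 1/(1 - d). The values of d are assumptions.

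| d | Median multiplied by |
|---|---|
| 5% | 1/0.95 = 1.05 |
| 10% | 1/0.90 = 1.11 |
| 15% | 1/0.85 = 1.18 |
| 20% | 1/0.80 = 1.25 |

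**Effect on the comparison.** If d is the same in both arms, each median is inflated but their ratio is not. If d is 5% in one arm and 15% in the other, with no true difference in progression or death, the ratio of medians becomes 0.95/0.85 = 1.12.

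**Number of responders.** With 150 patients at 1:1 there are 75 per arm.

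- Axitinib: the protocol's Table 3 gives 19.4% response in axitinib's approval trial, so 75 × 0.194 = 14.6, about 15.
- Combination: protocol 2.3.4.2 reports 5 partial responses among 17 evaluable phase 1b patients, 29%, so 75 × 5/17 = 22.1, about 22.

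These are different populations and indicate scale only. With 15 responders all followed to the end of response, one death without progression is 1/15 = 7% and two are 2/15 = 13%.

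**Noise at that size.** If all 15 and 22 responses end in an event, the 95% interval for a hazard ratio extends by a factor of exp(1.96 × √(1/15 + 1/22)) = exp(1.96 × 0.335) = 1.9 either way. A distortion of 1.12 lies well inside it.

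**Responders only.** A constructed example, with every duration assumed: the 19.4% who would respond on either treatment have a median duration of 11 months in both arms, and the combination adds further responders with shorter responses. Exponential mean = median / ln 2. A simulation with 30% to 40% responding on the combination, and medians of 5.5 to 8 months in the added responders, gave:

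- responders-only median: 7.5 to 9.8 months on the combination against 11 on control;
- mean time in response per randomised patient: 3.9 to 5.5 months against 3.1.

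By hand for one case (30% response, added median 5.5 months): control is 0.194 × 11/0.693 = 3.1, and the combination is 3.1 + 0.106 × 5.5/0.693 = 3.9. The responders-only result can point against a treatment that shortens nobody's response.

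**The case against.** A reader might infer more than the documents support, in four ways.

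- **That the plan instructs censoring at death.** It does not. Censoring follows from the literal definition, because progression is the only event. The statistician carrying out the analysis could handle deaths differently without contradicting any written rule. That is a gap in the text as much as an error in it.
- **That a formal test of duration is planned.** No test, alpha or hypothesis is named for it. The same paragraph names chi-square or Fisher tests for response rate, and SAP 11.1 names a log-rank test for PFS. The objective is to estimate. The phase 2 outputs in SAP 19.3 and 20.2 are a table and a listing, and the figure list in 20.3 has no curve for duration.
- **That the overstatement is known to be material, or favours the combination.** The documents give no rate of death during response, overall or by arm. One or two deaths among about 15 responders would be lost in the sampling error. The listings of time to progression or death and of fatal adverse events would let a careful reader find such patients.
- **That the primary result is at risk.** It is not; PFS has its own definition.

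All four limits stand. What survives them is that both documents define the endpoint by progression alone, say that it will be compared between arms, and place it in a population in which most patients may have no value for it.

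**Conclusion.** The point holds as a defect of definition and labelling in a secondary endpoint. Under the literal wording, responses ended by death without documented progression are censored, and the median is inflated by 1/(1 - d): 1.05 to 1.25 for d from 5% to 20%. That range rests on independent exponential hazards and on assumed death shares. The true effect may be small, and it distorts the contrast between arms only if the shares differ.

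That the by-arm comparison is confined to responders needs no assumption; it follows from the start of the clock. It is not a randomised comparison and conflicts with the ITT wording in SAP 3.2 and protocol 10.2.1. The size and direction of any selection effect are unknown; the example shows only that the sign can reverse.

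No alpha is attached to this endpoint, and neither the primary PFS test nor its 115 events are affected. The change should be made because it is nearly free and the present wording can mislead.

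**What to change.** 1. In SAP 11.1 and protocol 10.5.2, define duration of response as the time from first CR or PR to progression or death from any cause, whichever comes first.
2. Write out its censoring rules, using the SAP 11.1 rules for living patients without progression. A bare cross-reference to the PFS rules would not do in the protocol: its censoring sentence in 10.5.2 would bring back censoring of non-cancer and unknown-cause deaths and partly undo step 1. That sentence and SAP 11.1 must be reconciled in any case.
3. Label the by-arm Kaplan-Meier display as descriptive among responders.
4. Correct SAP 3.2 and the matching protocol text, in the synopsis and 10.2.1, so that duration of response is not described as an ITT analysis.
5. Optionally, if a between-arm comparison is wanted, add mean time in response over all randomised patients, counting non-responders as zero, up to a fixed horizon. This is a new estimand that needs its own horizon and censoring rules, and the correction does not depend on it.

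Steps 1 to 4 cost wording only and need no data beyond what PFS already requires. The reported duration becomes slightly shorter.
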